Subjects will be allocated to the cohorts by the study sponsor working in collaboration with each investigator considering the availability of openings for enrollment in Stage 1 or 2, disease type (i.e., FL, MZL, DLBCL-GCB, DLBCL-ABC, or other indications), therapy history (e.g., prior use of anti-CD20 or anti-PD1/PDL1 antibodies), and current disease status (e.g., potential to benefit from rituximab treatment based on past responses to anti-CD20 antibody therapy).

During Stage 1 dose ranging with LAM-002A monotherapy, allocation will be performed according to a 3+3 dose-escalation procedure with the requirement that each cohort of 3 subjects be observed for \geq 4 weeks before another cohort is enrolled (as detailed in Section 6.6). During Stage 2 cohort expansion evaluating LAM-002A monotherapy, allocation will be performed as subjects present to the accruing clinics and there will be no specific restrictions on the cadence of enrollment. During Stage 2 cohort-expansion of LAM-002A combinations with rituximab and atezolizumab, enrollment of the first 3 subjects in each combination cohort will be restricted such that each subject must be enrolled sequentially and observed for \geq 3 weeks before the next subject is enrolled. Beginning with the 4th patient in each combination group, further enrollment may proceed without restriction as long as the continuous reassessment boundaries for toxic drug discontinuations are not met (as detailed in Section 6.8.2.5 and Section 6.12).

Version 9, 18 Feb 2020

Section 6.1.4 Subject Evaluability

Change: This section was added to clarify subject evaluability for the dose-ranging and cohort-expansion portions of the study.

A Stage 1 subject will be considered evaluable if the subject meets the definition for evaluability of Cycle 1 DLT as described in Section 6.6. A Stage 2 subject will be considered evaluable if the subject has both baseline and ≥ 1 on-study tumor assessments sufficient to allow a determination of response to study therapy.

Section 6.2. Number of Subjects

Change: The number of subjects was updated to reflect the new dose-escalation and cohort-expansion plans.

As many as 110 Approximately 115 evaluable subjects (evaluable subjects include those who complete Cycle 1 dosing [administered at least 75% of doses] and have sufficient safety data, or who are withdrawn from the study due to a DLT in Cycle 1) will be enrolled, assuming that:

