Change: The protocol was modified to permit evaluation of single-agent LAM-002A or the LAM-002A/rituximab combination in additional patients with FL. Use of either intravenously administered rituximab or subcutaneously administered rituximab hyaluronidase human was permitted.

Once the MTD and/or recommended phase 2 dose (RP2D) and schedule is determined, the study will enter the expansion stage, in which cohorts of subjects will be accrued in order to obtain additional information on safety, tolerability, preliminary anti-tumor activity, PK, and pharmacodynamic data at the RP2D and schedule when LAM-002A is administered alone or in combination with rituximab/rituximab hyaluronidase or atezolizumab. Expansion-stage cohorts will comprise groups of subjects with specific types of previously treated, relapsed, progressive, and measurable NHL who will receive LAM-002A monotherapy or LAM-002A-containing combination therapy as shown in Table 2. For both monotherapy and combination cohorts, the starting dose of LAM-002A will be 125 mg BID administered continuously.

Version 9, 18 Feb 2020

Table 2: Expansion Stage Disease Types and Therapies

Cohort Number	NHL Type	Investigational Drug	Combination Drug	Evaluable Subjects, n
1	FL	LAM-002A		6 Up to ~20
2	MZL	LAM-002A		6
3	DLBCL-GCB	LAM-002A		6
4	DLBCL-ABC	LAM-002A		6
5	FL or MZL	LAM-002A	Rituximab or rituximab hyaluronidase human	6 Up to ~20 with FL
6	DLBCL-GCB or DLBCL-ABC	LAM-002A	Rituximab or rituximab hyaluronidase human	6
7	FL or MZL	LAM-002A	Atezolizumab	6
8	DLBCL-GCB or DLBCL-ABC	LAM-002A	Atezolizumab	6

Abbreviations: ABC: activated B-cell (subtype); DLBCL: diffuse large B-cell lymphoma; FL: follicular lymphoma; GCB: germinal center B-cell (subtype); MZL: marginal zone lymphoma; NHL: non-Hodgkin lymphoma

Section 6.2 Number of Subjects

Change: Information regarding the total potential accrual to the study was updated consistent with modifications to the protocol to evaluate single-agent LAM-002A or the LAM-002A/rituximab combination in additional patients with FL.

As many as $\underline{145}$ $\underline{110}$ subjects will be enrolled, assuming that:

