As noted above, the target ORR with LAM-002A alone is ~40%. Adding rituximab or rituximab hyaluronidase human to LAM-002A would be expected to enhance the ORR over that associated with single-agent LAM-002A. Thus, the combination of LAM-002A/rituximab could warrant further development if an ORR of \geq 60% could be targeted in preference to an ORR of < 40%. Accordingly, for combination therapy, sequential boundaries will be used to continuously monitor that the ORR is \geq 60% while excluding an ORR of 39% using a 1-sided test with a significance level of 0.05. A significant result with this testing would conclude with 95% confidence that the actual ORR is \geq 39%. Accrual of up to \sim 20 evaluable subjects will be considered with the potential to stop accrual early if the boundary is crossed. Thus, accrual can be considered sufficient if the following n/N values are observed: 7/10, 8/11, 8/12, 9/13, 9/14, 10/15, 10/16, 11/17, 11/18, 12/19, 12/20. For all these values, the ORR is \geq 60% with a lower 1-sided binomial confidence bound of \geq 39%.

Experience indicates the rates of discontinuations from rituximab or atezolizumab therapy are < 5% (Genentech 2016, Genentech 2017). A rate of AE discontinuations of therapy due to adverse events of \geq 25% in the 2 combination therapy groups of LAM-002A/rituximab (N = 12) or LAM-002A/atezolizumab (N = 12) would suggest a potential adverse interaction among the components of the combination therapy. Sequential Pocock-type boundaries will be used to continuously monitor the rate of AE discontinuations and to test the null hypothesis, after each subject, that the event rate is \geq 0.25 using a 1-sided significance test of \sim 0.05. AE discontinuation rates will be considered excessive if the following n/N values are observed: -/1, -/2, 3/3, 3/4, 4/5, 4/6, 5/7, 5/8, 5/9, 6/10, 6/11, 7/12. With this method, the probability of detecting an AE discontinuation safety signal ranges from 0.091 to \geq 0.820 for true discontinuation rates of 25% to \geq 60%. If excessive levels of AE discontinuation are observed, the sponsor, working in collaboration with the cooperating companies and investigators, will take appropriate actions (eg, continuation of the cohort with modifications in design or monitoring plan, interruption of cohort accrual, cohort therapy discontinuation).

Version 9, 18 Feb 2020

Section 22. List of References

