Changes: Text was included to explain the addition of an extension stage to the study.

The extension stage (Stage 3) can begin once the last study subject has completed at least 8 cycles of study treatment. At this time, the study sponsor will conclude the dose-escalation and expansion stages of the study, will collate and verify all study data through an appropriate data cutoff date, and will lock the study database for preparation of a study report. Subjects who are still safely benefiting from Stage 1 or Stage 2 study therapy as of the data cutoff date may electively continue their current regimen of study therapy in Stage 3, receiving clinical care and diagnostic testing consistent with conventional practice standards as deemed appropriate by the treating investigator. Therapy in Stage 3 may continue in the absence of protocol-defined reasons to discontinue therapy. During Stage 3, collection of clinical data by the sponsor will be limited to serious adverse event (SAE) reports. Study drug accountability will be managed per site procedures; relevant pharmacy records may be collected by the sponsor to document study drug disposition.

Section 6.2. Number of Subjects

Changes: Text was included consistent with addition of an extension stage to the study.

As many as 145 subjects will be enrolled, assuming that:

- In the dose-escalation stage of the study, the total number of subjects will depend upon the numbers of subjects accrued to each dose level and the number of dose levels evaluated. If 6 subjects are enrolled at all open starting dose levels (Dose Levels 5, 6, 7, and 8) and 6 additional subjects are enrolled at the MTD or RD, as many as 30 subjects could be enrolled. To allow for the possibility that some subjects may not be fully evaluable for DLT or that an intermediate dose level might be evaluated, up to ~45 subjects may be enrolled.
- In the expansion stage of the study, if all 8 potential expansion cohorts are accrued, as many as ~76 subjects could be enrolled. To allow for the possibility that some subjects may not be fully evaluable for efficacy or to establish bounds on efficacy estimates with greater confidence, up to ~100 subjects may be enrolled.

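### The AE-discontinuation boundary for LAM-002A/rituximab still ends at 12 subjects, although the same amendment lets that group grow to about 26

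*Combined protocol and SAP*

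**What the plan says.** The amendment that enlarged the FL cohorts changes Section 6.1.2 so that the study can evaluate single-agent LAM-002A or "the LAM-002A/rituximab combination in additional patients with FL". In its Table 2, cohort 5 (LAM-002A with rituximab) goes from 6 to "Up to ~20 with FL". Cohort 6 (DLBCL with rituximab) and both atezolizumab cohorts stay at 6. Section 6.2 gives the matching expansion total: "as many as ~76 subjects could be enrolled".

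The same amendment's Section 14.1.2 adds response-rate boundaries for the FL combination, running from 7/10 to 12/20. The next paragraph, on discontinuations for adverse events, still refers to a signal "in the 2 combination therapy groups of LAM-002A/rituximab (N = 12) or LAM-002A/atezolizumab (N = 12"). The null is "that the event rate is \geq 0.25 using a 1-sided significance test of \sim 0.05", and the list reads "1, -/2, 3/3, 3/4, 4/5, 4/6, 5/7, 5/8, 5/9, 6/10, 6/11, 7/12". The probability of a signal "ranges from 0.091 to \geq 0.820 for true discontinuation rates of 25% to \geq 60"%.

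Section 6.1.3 (Amendment 6) ties enrolment to this list. From the fourth subject in each combination group, "further enrollment may proceed without restriction as long as the continuous reassessment boundaries for toxic drug discontinuations are not met".

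**The concern.** The list stops at 12 because the rituximab group was then two cohorts of 6. The amendment extended efficacy monitoring to the new cohort size but left the safety count where it was. Beyond subject 12 the enrolment condition refers to a boundary with no value, so it can neither be met nor missed.

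This rule is the plan's pre-specified check on whether the combination produces an excessive rate of AE discontinuations. If the excess is moderate, 12 subjects often will not show it, and the later subjects who could show it are not counted against any threshold. The stated probabilities may also be read as applying to the enlarged group.

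**Working it through.** **Group size.** From Table 2 as amended, the eight cohorts are 20 + 6 + 6 + 6 + 20 + 6 + 6 + 6 = 76, which matches Section 6.2. The rituximab group is 20 + 6 = 26. Beyond the last boundary value: 26 − 12 = 14, and 14/26 = 54%. The atezolizumab group is 6 + 6 = 12, fully covered.

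**Reproducing the plan's figures.** Let b(n) be the listed boundary and p the true discontinuation rate. After each subject, update the binomial distribution of the event count, remove the paths with count ≥ b(n), and add their probability to the crossing total. At p = 0.25 the first-crossing probabilities are:

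- n = 3: 0.25³ = 0.0156
- n = 4: 3 × 0.25² × 0.75 × 0.25 = 0.0352
- n = 6, 8, 9, 11: 0.0132, 0.0066, 0.0145, 0.0057
- n = 5, 7, 10, 12: zero, because the boundary rises by one at each of these

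The sum is 0.0908, against the stated 0.091. The same recursion at p = 0.60 gives 0.8201, against the stated 0.820. Both figures therefore belong to monitoring that ends at 12 subjects.

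**Recovering the rule.** Each listed value is the smallest k with P(X ≥ k | n, 0.25) no greater than 0.0508, the tail at 3/4. The plan's figure of about 0.05 is thus the per-look level, and 0.091 is the overall crossing probability at 25%.

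**Carrying the same rule to 26.** This adds 7/13, 7/14, 8/15, 8/16, 8/17, 9/18, 9/19, 9/20, 10/21, 10/22, 10/23, 11/24, 11/25 and 11/26. Crossing probabilities:

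| True rate | Rule ends at 12 | Carried to 26 |
|---|---|---|
| 10% | 0.005 | 0.005 |
| 25% | 0.091 | 0.130 |
| 30% | 0.160 | 0.257 |
| 40% | 0.364 | 0.615 |
| 50% | 0.609 | 0.892 |
| 60% | 0.820 | 0.987 |

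**Holding the crossing probability at 25% near 0.091.** Over 26 looks this needs a per-look level of about 0.036 to 0.038, which gives 0.086 to 0.094. Detection is then about 0.53 to 0.54 at 40% and 0.85 at 50%. Some early values change: 3/4 becomes 4/4 and 5/9 becomes 6/9; at the lower level 4/6 also becomes 5/6.

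**If FL accrual stops early.** The earliest response boundary is 7/10. With cohort 6 full, the group is then 10 + 6 = 16, with 4 (25%) beyond subject 12. Assuming accrual stops at the first response crossing and cohort 6 fills, the expected group size is 25.2 (52% beyond subject 12) at a true ORR of 40%, 23.4 (49%) at 50% and 20.7 (42%) at 60%. With the extended boundary, detection at a 40% discontinuation rate is 0.44 if the group ends at 16 and 0.53 if it ends at 20.

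**The case against.** A reader might infer that later subjects are treated with no safety rule. The documents do not support that. LAM-002A dose modification (Section 6.8.2.5), rituximab interruption and discontinuation (Section 6.8.3.4), withdrawal for unacceptable toxicity (Section 6.12) and 24-hour SAE/AESI reporting with medical-monitor review (Section 10.6) cover every subject. A long run of discontinuations after subject 12 would therefore not go unseen. What is missing is a pre-specified threshold for the group's rate, and none of those provisions supplies one.

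A reader might also infer that more than half of the group is necessarily uncovered. That holds only at or near full accrual. About 26 is a ceiling, and at the protocol's target ORR of 60% the expected share is 42%.

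It can be argued that 12 subjects were all the interaction question was meant to need, and that a crossing only prompts the sponsor to choose among several actions, the first being continuation with modifications. The second part is correct and limits the consequence. The first is not stated anywhere, and it does not fit an enrolment condition that has no end point.

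Finally, the available part of the document holds amendment summaries; the running text of Sections 6.1.3 and 14.1.2 is in the other part. However, the enlarged Table 2 and the unchanged N = 12 come from one amendment, and the later amendment, as far as it is shown, does not alter the rule. That later amendment also expects fewer than 4 subjects in the extension stage, so the expansion may be largely complete and the prospective benefit small.

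**Conclusion.** The concern holds in a limited form. For LAM-002A/rituximab only, the AE-discontinuation boundary and its stated operating characteristics cover 12 subjects, while the plan allows about 26. Between 4 of 16 (earliest FL stop, cohort 6 full) and 14 of 26 (full accrual) would enter with no group-level discontinuation boundary, and the enrolment condition in Section 6.1.3 cannot be applied to them. At a true 40% rate the rule as written signals with probability 0.364; carried to 26 subjects it would be 0.615.

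These figures assume independent subjects with a constant rate and a count updated after each subject. The comparison at 26 assumes full accrual. The conclusion also assumes that the running text agrees with the amended text.

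**What to change.** In Section 14.1.2, replace N = 12 for LAM-002A/rituximab with the Table 2 figure (about 26), extend the boundary to that N and restate the crossing probabilities. Leave the atezolizumab group at 12. Two ways to extend:

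- **Keep the existing per-look level** (at most about 0.051 under 25%). The values to 12 stand, and the fourteen values from 7/13 to 11/26 above are added. The cost is a crossing probability at 25% of 0.130 instead of 0.091.
- **Hold the crossing probability at 25% near 0.091** with a per-look level of about 0.036 to 0.038. The cost is lower detection than the first option (about 0.53 to 0.54 against 0.615 at 40%) and changes to some values already in the list.

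Either way, check that the condition in Section 6.1.3 points to the extended list. No extra subjects, visits or procedures are needed, and a false alarm leads to sponsor review, not an automatic stop.

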Changes: Text was included to explain the addition of an extension stage to the study.

The extension stage (Stage 3) can begin once the last study subject has completed at least 8 cycles of study treatment. At this time, the study sponsor will conclude the dose-escalation and expansion stages of the study, will collate and verify all study data through an appropriate data cutoff date, and will lock the study database for preparation of a study report. Subjects who are still safely benefiting from Stage 1 or Stage 2 study therapy as of the data cutoff date may electively continue their current regimen of study therapy in Stage 3, receiving clinical care and diagnostic testing consistent with conventional practice standards as deemed appropriate by the treating investigator. Therapy in Stage 3 may continue in the absence of protocol-defined reasons to discontinue therapy. During Stage 3, collection of clinical data by the sponsor will be limited to serious adverse event (SAE) reports. Study drug accountability will be managed per site procedures; relevant pharmacy records may be collected by the sponsor to document study drug disposition.

Section 6.2. Number of Subjects

Changes: Text was included consistent with addition of an extension stage to the study.

As many as 145 subjects will be enrolled, assuming that:

- In the dose-escalation stage of the study, the total number of subjects will depend upon the numbers of subjects accrued to each dose level and the number of dose levels evaluated. If 6 subjects are enrolled at all open starting dose levels (Dose Levels 5, 6, 7, and 8) and 6 additional subjects are enrolled at the MTD or RD, as many as 30 subjects could be enrolled. To allow for the possibility that some subjects may not be fully evaluable for DLT or that an intermediate dose level might be evaluated, up to ~45 subjects may be enrolled.
- In the expansion stage of the study, if all 8 potential expansion cohorts are accrued, as many as ~76 subjects could be enrolled. To allow for the possibility that some subjects may not be fully evaluable for efficacy or to establish bounds on efficacy estimates with greater confidence, up to ~100 subjects may be enrolled.
- In the extension stage of the study, the total number of subjects will include <4 subjects who have participated in the expansion stage of the study and are still receiving study therapy on the data cutoff date that concludes the dose-escalation and expansion stages of the clinical trial.

Version 9, 18 Feb 2020

Section 6.5.2. Treatment Period

Changes: Text was removed consistent with addition of an extension stage to the study.

The subject is treated and monitored for safety (including assessments of AEs, vital signs, ECGs, laboratory tests and concomitant medications). Additionally, preliminary anti-tumor activity will be assessed and PK and biomarker samples will be collected. In the absence of protocol defined reasons to discontinue therapy, subjects may continue to receive study treatment for up to 1 year at the discretion of the investigator and beyond 1 year with the agreement of the investigator and the sponsor.

Section 8. Methods of Assessment and Endpoints

Changes: Text was included consistent with addition of an extension stage to the study.

All trial data during the dose-escalation stage (Stage 1) and expansion stage (Stage 2) will be recorded on the eCRFs. Timing of study procedures for the dose-escalation stage (Stage 1) and expansion stage (Stage 2) are listed in schedules of assessments tables – Table 8: Schedule of Assessments (LAM-002A Continuous Monotherapy Administration), Table 9: Schedule of Assessments (LAM-002A Intermittent Monotherapy Administration), Table 10: Schedule of Assessments (LAM-002A/Rituximab Combination Therapy), and Table 11: Schedule of Assessments (LAM-002A/Atezolizumab Combination Therapy) – in Section 8.7. During the extension stage (Stage 3), collection of clinical data by the sponsor will be limited to serious adverse event (SAE) reports. Study drug accountability will be managed per site procedures; relevant pharmacy records may be collected by the sponsor to document study drug disposition.

Section 9.1.6. Handling and Disposal

Changes: In the context of transitioning to the extension stage of the study, site monitoring of drug accountability by the contract research organization, Ce3, was discontinued.

LAM-002A accountability and inventory records will be inspected by the sponsor/Ce³ prior to final disposition. Instructions will be provided by the sponsor/Ce³ for shipment to and destruction of unused LAM-002A product by the designated packaging depot, to include unopened bulk bottles at the end of the study and expired product. Unused product returned by study subjects or opened bulk bottles will be destroyed by each site per site SOPs. LAM-002A should only be shipped or destroyed upon written authorization from the sponsor/Ce³. Documentation of return of shipment, including a packing list and copy of the tracking label, should be retained in the Pharmacy and/or regulatory files.

Section 10.6. SAE and AESI Reporting

Changes: In the context of transitioning to the extension stage of the study, pharmacovigilance monitoring of SAEs was transitioned from the contract research organization, Pharmalex, Inc. to the study sponsor, AI Therapeutics.

- The investigator is obligated to immediately report to Pharmalex, Inc. AI Therapeutics each SAE and each AESI that occurs during this investigation, within 24 hours from knowledge of the event, whether or not it is considered study-drug related.
- All requested supplementary documents (e.g., discharge summary, autopsy report) and relevant data (e.g., ECGs, laboratory tests, discharge summaries, post mortem results) must

Protocol: LAM-002A-NHL-CLN01 Version 9, 18 Feb 2020

be faxed or emailed within 24 hours to

The information provided in a SAE or AESI report should be as complete as possible, but contain a minimum of the following:

- A short description of the AE (diagnosis) and the reason why the AE was categorized as an SAE or AESI
- Subject identification and treatment
- Investigator's name and telephone number (if applicable)
- Name of the suspect medicinal product and dates of administration
- Assessment of causality.

If any questions or considerations regarding SAE or AESI report requirements or report completion arise, the principal investigator/site staff should contact PharmaLexAI Therapeutics. Medically related questions or concerns regarding treatment should be directed to the sponsor's medical monitor.

If all information about the SAE or AESI is not yet known, the investigator will be required to report any additional information within 24 hours as it becomes available. SAEs and AESIs must be followed and reported upon until the event has completely resolved to Grade 0 or baseline or until the event becomes a new stable baseline condition for a subject.

All SAEs and AESIs will be evaluated by the sponsor's medical monitor or designee.

The investigators must notify their governing IRB of any SAEs in accordance with Section 18.1.

For any suspected adverse reaction that is both serious and unexpected (not documented in the IB or package insert), an Investigational New Drug (IND) safety report or revision to the IB may be issued to inform all investigators involved in any study with LAM-002A.

Section 10.7. Pregnancy Reporting

Changes: In the context of transitioning to the extension stage of the study, pharmacovigilance monitoring of pregnancy was transitioned from the contract research organization, Pharmalex, Inc. to the study sponsor, AI Therapeutics.

Pregnancy occurring in a subject is not considered an AE. However, the investigator must capture pregnancy information for subject and/or subject's partner (as applicable) on a pregnancy report form within 24 hours of learning of the pregnancy. Then the site

- Completes the pregnancy form with as much information as possible; however, at a
 minimum the subject identification number, name of product, and name of reporter is
 required;
- Signs Pregnancy Notification form; and
- FAX the form to

Subjects determined to be pregnant must be immediately removed from treatment and will be followed by the investigator until termination of the pregnancy or delivery of the child.

Version 9, 18 Feb 2020

Additional information on the course of the pregnancy should be supplied on follow-up forms as it becomes available and at minimum at termination or birth.

Section 10.7. 14.1.3 Extension Stage (Stage 3)

Changes: Text was included in the statistical section of the protocol consistent with addition of an extension stage to the study.

The sample size in the extension stage of the study will be no higher than the total number of subjects on study therapy on the data cutoff date that concludes the dose-escalation and expansion stages of the clinical trial.

Section 16. Study Monitoring

Changes: Text was included consistent with the plan to discontinue regular monitoring of study sites during the extension stage of the study.

Before an investigational site can enter a subject into the study, a representative of AI Therapeutics will visit the investigational study site to:

- Determine the adequacy of the facilities
- Discuss with the investigator and other personnel their responsibilities with regard to protocol adherence, and the responsibilities of AI Therapeutics or its representatives. This will be documented in a Clinical Study Agreement between AI Therapeutics and the investigator.

During the study, a monitor from AI Therapeutics or its representative will have regular contacts with the investigational site for the following:

- Provide information and support to the investigator
- Confirm that facilities remain acceptable
- Confirm that the investigational team is adhering to the protocol that data are being accurately recorded in the eCRFs, and that investigational product accountability checks are being performed
- Perform source data verification. This includes a comparison of the data in the CRFs with the subject's medical records at the hospital or practice, and other records relevant to the study. This will require direct access to all original records for each subject (e.g., clinic charts)
- Record and report any protocol deviations not previously sent to AI Therapeutics
- Confirm AEs and SAEs have been properly documented on eCRFs, and confirm any SAEs have been forwarded to AI Therapeutics and those SAEs that met criteria for reporting have been forwarded to the IRB

The monitor will be available between visits if the investigator or other staff members need information or advice.

Upon conclusion of the Dose-Escalation (Stage 1) and Expansion (Stage 2) stages of the study, routine site monitoring by AI Therapeutics or its representatives will be discontinued.
